7.3.3 Reporting to Eli Lilly

- To comply with applicable laws, regulations and standards regarding Investigator's and Institution's obligations, as the sponsor of the Study, to collect and report adverse events to regulatory authorities, IRBs, Ethics Committees or other third parties. In addition to the obligations set forth below, Investigator and Institution agree to provide Lilly with a copy of all information Investigator and/or Institution submit to regulators related to any adverse events for the Study Drug that occur during the Study that Investigator and/or Institution have not otherwise provided Lilly;
- To notify Lilly, sub-investigators, and the IRB of any problems involving risk to Study patients and report new safety information to IRBs in accordance with applicable requirements;
- Notify Lilly within fifteen (15) business days of Investigator and/or Institution receiving notification of any “serious” adverse event experienced by a patient participating in the Study and receiving Study Drug. For purposes of this requirement, “serious” means: (1) death; (2) in-patient hospitalization or prolonged hospitalization; (3) life-threatening; (4) persistent or significant disability or incapacity; (5) congenital anomaly or birth defect; or (6) other serious events that may jeopardize the patient and may require medical or surgical intervention to prevent one of the other five listed outcomes. Serious adverse events should be reported to Lilly using a CIOMS Form or other form acceptable to Lilly. Investigator and Institution further agree to make available promptly to Lilly such records as may be necessary and pertinent for Lilly to further investigate an adverse event in the Study that is possibly associated with the Study Drug.
- **SAE Reporting Email Address:** [contact]
 - The Mandatory MedWatch Form 3500A can be used for SAE reporting

7.3.4 Reporting to Merck

Any serious adverse event, or follow up to a serious adverse event, deemed related to study procedures from the time of consent up to study drug initiation, must be reported within 24 hours to the Sponsor (DFCI) and within 2 working days to Merck Global Safety. Any serious adverse event, or follow up to a serious adverse event, including death due to any cause other than progression of the cancer under study, that occurs to any subject from the time of study drug initiation through 90 days following cessation of treatment, or the initiation of new anti-cancer therapy, whichever is earlier, whether or not related to Merck product, must be reported within 24 hours to the Sponsor (DFCI) and within 2 working days to Merck Global Safety.

Non-serious Events of Clinical Interest will be forwarded to Merck Global Safety and will be handled in the same manner as SAEs.

Additionally, any serious adverse event, considered by an investigator who is a qualified physician to be related to Merck product that is brought to the attention of the investigator at any time outside of the time period specified in the previous paragraph also must be reported immediately to the Sponsor and to Merck.

SAE reports and any other relevant safety information are to be forwarded to the Merck Global Safety [contact]

A copy of all 15 Day Reports and Annual Progress Reports is submitted as required by FDA, European Union (EU), Pharmaceutical and Medical Devices agency (PMDA) or other local regulators. Investigators will cross reference this submission according to local regulations to the Merck Investigational Compound Number (IND, CSA, etc.) at the time of submission. Additionally, investigators will submit a copy of these reports to Merck & Co., Inc. (Attn: Worldwide Product Safety; [contact]) at the time of submission to FDA.

All subjects with serious adverse events must be followed up for outcome.

7.3.5 Reporting to the Food and Drug Administration (FDA)

The Overall PI, as study sponsor, will be responsible for all communications with the FDA. The Overall PI will report to the FDA, regardless of the site of occurrence, any serious adverse event that meets the FDA's criteria for expedited reporting following the reporting requirements and timelines set by the FDA.

For expedited reporting, AEs for the agent(s) that are listed above should be reported only if the adverse event varies in nature, intensity or frequency from the expected toxicity information which is provided. should AEs that vary in nature, intensity or frequency from the expected toxicity information provided in the protocol and the investigator brochure.

7.3.6 Reporting to Hospital Risk Management

Participating investigators will report to their local Risk Management office any participant safety reports, sentinel events or unanticipated problems that require reporting per institutional

policy.

7.3.7 Routine Adverse Event Reporting

All Adverse Events **must** be reported in routine study data submissions to the Overall PI on the toxicity case report forms. **AEs reported through expedited processes (e.g., reported to the IRB, FDA, etc.) must also be reported in routine study data submissions.**

8. PHARMACEUTICAL INFORMATION

A list of the adverse events and potential risks associated with the investigational agents administered in this study can be found in Section 7.1.

8.1 Abemaciclib

8.1.1 Description

Abemaciclib, (IUPAC: N-[5-[(4-ethylpiperazin-1-yl)methyl]pyridin-2-yl]-5-fluoro-4-(7-fluoro-2-methyl-3-propan-2-ylbenzimidazol-5-yl)pyrimidin-2-amine), or LY2835219, is a potent and selective inhibitor of CDK4 and CDK6 with IC₅₀ of 2 nM and 10 nM, respectively. It has a molecular weight of 602.7 and its chemical formula is C₂₈H₃₆F₂N₈O₃S.

The half-life is 17-38 hours. Metabolism is primarily hepatic and dependent on CYP3A4. Three major metabolites of abemaciclib, M2, M18 and M20, are found at a concentration > 10% of the parent drug. Those also exert inhibition of CDK4/6 and undergo hepatic metabolism.

Abemaciclib and its metabolites are bound to human plasma proteins: 96.3% for abemaciclib, 93.4% for M2, 96.8% for M18, and 97.8% for M20. Abemaciclib is also a substrate of P-gp and BCRP in vitro, but the effect of P-gp or BCRP inhibitors on abemaciclib are unknown. The geometric mean systemic volume of distribution is approximately 690.3 L (49% CV). Concentration of abemaciclib and metabolites M2 and M20 in cerebrospinal fluid are similar to unbound plasma concentration.

Abemaciclib, M2 and M20, do not induce CYP1A2, CYP2B6, or CYP3A4 at clinically relevant concentrations. Abemaciclib, M2 and M20, down regulate mRNA of CYP1A2, CYP2B6, CYP2C8, CYP2C9, CYP2D6 and CYP3A4. The mechanism and clinical relevance of this down regulation are not understood, but no time-dependent changes in abemaciclib concentration due to inhibition of CYP3A4 has been observed.

Based on evaluation of the QTc interval in patients and in a healthy volunteer study, abemaciclib did not cause large mean increases (i.e., 20 ms) in the QTc interval.

8.1.2 Form

Abemaciclib, manufactured by Eli Lilly and Company, will be provided in the form of 50mg tablets in a bottle.

Inactive ingredients are as follows:

- Excipients: microcrystalline cellulose 102, microcrystalline cellulose 101, lactose monohydrate, croscarmellose sodium, sodium stearyl fumarate, silicon dioxide.
- Color mixture ingredients: polyvinyl alcohol, titanium dioxide, polyethylene glycol, talc, iron oxide yellow, and iron oxide red.

8.1.3 Storage and Stability

Abemaciclib needs to be stored in the original package. Abemaciclib needs to be kept at room temperature.

8.1.4 Handling

Qualified personnel, familiar with procedures that minimize undue exposure to themselves and the environment, should undertake the preparation, handling, and safe disposal of the chemotherapeutic agent in a self-contained and protective environment.

8.1.5 Availability

Abemaciclib will be provided for clinical trial use as 50mg tablets by Eli Lilly and Company. Storage conditions are described in the medication label.

8.1.6 Administration

Abemaciclib will be taken orally every 12 (\pm 2) hours with or without food. Tablets should not be crushed, chewed or dissolved. During all cycles, abemaciclib should be taken at approximately the same times each day. If a patient misses or vomits a dose, that dose should be omitted.

8.1.7 Ordering

Eli Lilly and Company will supply abemaciclib and ordering will take place through Eli Lilly and Company. The study team will complete the Drug Request Form, which is kept as a separate document.

8.1.8 Accountability

The investigator, or a responsible party designated by the investigator, should maintain a careful record of the inventory and disposition of the agent using the NCI Drug Accountability Record Form (DARF) or another comparable drug accountability form. (See the NCI Investigator's Handbook for Procedures for Drug Accountability and Storage.)

8.1.9 Destruction and Return

Drug should be destroyed at the site, after the investigator approves the drug destruction policy at the site. Drug will not be returned to Eli Lilly and Company. Destruction will be documented in the Drug Accountability Record Form.

8.2 MK-6482

8.2.1 Description

MK-6482 is a potent selective inhibitor of HIF-2 α . Mean half-life of MK-6482 is 22.5 hours. MK-6482 oxidative metabolism is minimal in most species. No CYP450 enzyme reaction phenotyping has been performed. One glucosidic glucuronide metabolite detected in rats and dogs (PT3317) was found to be dependent on UGT2B17, mainly expressed in the small intestine.

MK-6482 do not inhibit any CYP enzymes by either competitive (7 CYP isoforms) or time-dependent (CYP3A4) mechanisms up to at least 50 μ M. MK-6482 however increase production of CYP3A4 mRNA in cultured human hepatocytes with a half-maximal effective concentration (EC₅₀) of 9.63 to 12.2 μ M. The mean C_{max} value for the clinical dose of 120 mg is about 2-fold less than the concentrations at which CYP induction effects are observed.

8.2.2 Form

MK-6482, manufactured by Merck, will be provided in the form of 40mg oblong tablets for oral administration.

Each MK-6482 Tablet contains MK-6482 formulated as a spray-dried dispersion with hydroxypropyl methylcellulose acetate succinate, microcrystalline cellulose, mannitol, croscarmellose sodium, and magnesium stearate.

8.2.3 Storage and Stability

MK-6482 must be stored in a secure location in accordance with the study drug label.

8.2.4 Handling

Qualified personnel, familiar with procedures that minimize undue exposure to themselves and the environment, should undertake the preparation, handling, and safe disposal of the chemotherapeutic agent in a self-contained and protective environment.

8.2.5 Availability

MK-6482 will be provided for clinical trial use as 40mg tablets by Merck Storage conditions are described in the medication label.

8.2.6 Administration

MK-6482 will be taken orally every approximately 24 hours. Patients should not consume food beginning 2 hour before and ending 1 hour after taking MK-6482. MK-6482 tablets should not be crushed, chewed or dissolved in water. Missed doses of MK-6482 may be made up if taken within 12 hours after the scheduled administration time. Patients who vomit after study drug administration should not retake that study drug dose but should resume taking study drug at the next scheduled administration time.

8.2.7 Ordering

Merck will supply MK-6482 and ordering will take place through Merck. The study team will complete the Drug Request Form, which is kept as a separate document.

8.2.8 Accountability

The investigator, or a responsible party designated by the investigator, should maintain a careful record of the inventory and disposition of the agent using the NCI Drug Accountability Record Form (DARF) or another comparable drug accountability form. (See the NCI Investigator's Handbook for Procedures for Drug Accountability and Storage.)

8.2.9 Destruction and Return

Drug should be destroyed at the site, after the investigator approves the drug destruction policy at the site. Drug will not be returned to Merck. Destruction will be documented in the Drug Accountability Record Form.

9. BIOMARKER STUDIES

Exploratory correlative studies will be performed to assess potential predictors of response to abemaciclib and abemaciclib plus MK-6482. Tissue samples, and whole blood for germline DNA, will be analyzed by investigators at DFCI and collaborating institutions, such as the Broad Institute (Harvard/MIT, Boston), for all patients enrolled on this trial.

Rapid progress in understanding and treating cancer will occur when some of the genetic information derived from tissues and blood can be shared with other researchers. In particular, the National Institutes of Health (NIH) and other organizations have developed special data (information) repositories that analyze data and collect the results of certain types of genetic studies. These central banks will store genetic information, and provide them to qualified researchers to do more research. Therefore, we may share results with these public databases. Some of this information may be made available over the internet and will be freely available to anyone who is interested (an open access database). Other, more detailed information may only be accessed by scientists at other research centers who have received special permission to review study participants' de-identified data (a controlled access database).

Study participant's information will be sent only with a code number attached. Name or other directly identifiable information will not be shared with these repositories or with other investigators. There are many safeguards in place to protect participant's information while they are stored in these repositories and used for research. There is a slight risk of loss of privacy when sharing this information with these banks but we have established procedures to encode study participant information and to protect participant data. The repositories also have robust procedures in place to protect the confidentiality of the stored data. We will do everything we can to protect study participant's data but we cannot absolutely guarantee its privacy or predict how genetic information will be used in the future.

9.1 Blood studies

9.1.1 Blood collection

Blood will be collected at baseline, Cycle 1 Day 1 and Cycle 1 Day 15. For DF/HCC participating sites, 30 mL of blood will be collected as per the Laboratory Manual and couriered within 6 hours of collection to The Gelb Center for Translational Research. For non-DF/HCC participating sites, 30 mL of blood will be collected at baseline and stored as per the Laboratory Manual and batch shipped at the end of study to The Gelb Center for Translational Research.

9.1.2 Procedures

Germline DNA

Germline DNA from whole blood will be used as control for molecular studies. It will also be used to evaluate clonal hematopoiesis of indeterminate potential and correlate this parameter with outcomes.

Circulating biomarkers

Serum plasma will be collected. Plasma will be collected to analyze candidate circulating biomarkers including cytokines and chemokines and their evolution on treatment.

Cell-free circulating DNA

Quantitative detection of cell-free circulating tumor DNA will be evaluated during the course of the study, and correlated with outcomes.

9.2 Tissue studies

9.2.1 Tissue collection

Archival tissue will be retrieved if available. Patients will undergo mandatory baseline tumor biopsy (unless medically unsafe), and post-treatment tumor biopsy after progression, in case of initial response (unless medically unsafe).

Archived tumor tissue collected pre-study as per the Laboratory Manual will be stored at ambient temperature and shipped quarterly to the [name] Laboratory, Brigham and Women's Hospital, Boston.

Frozen specimens from tumor biopsies will be stored at -80°C, and specimens fixed in formalin will be stored at 4°C until shipping. The tumor specimens will be shipped to the [name] Laboratory quarterly.

Fresh tissue from biopsy specimens will be collected as stated in this protocol and according to institutional guidelines, and put on ice to be transported to the processing laboratory or cryopreserved. A portion of fresh tissue will be dissociated into a single cell suspension and frozen for future studies, including but not limited to single cell transcriptomic, epigenetic, and proteomic studies, and cell line creation.

9.2.2 Procedures

Molecular profiling

Mutation profiling will be performed using massively parallel sequencing technology and a targeted gene panel (Oncopanel) and/or whole exome and/or whole genome sequencing. Gene expression signatures will be explored with whole transcriptome sequencing. The sequencing data will be analyzed for somatic mutations, copy number alterations, overexpressed genes, and chimeric transcripts and a complete set of potential driver alterations will be compiled in archival tissue, in baseline biopsies, and in biopsies performed at progression.

Immunostaining

Immunohistochemistry, immunofluorescence, and/or other advanced imaging techniques will be used to determine the expression of cell cycle genes in tumor cells. Other candidate biomarkers of response to therapy may be explored.

10. PHARMACOKINETIC AND PHARMACODYNAMIC STUDIES

10.1 Pharmacokinetic Assessments

Blood samples for the determination of plasma abemaciclib, abemaciclib metabolites, MK-6482, and MK-6482 metabolites will be collected at multiple time points throughout the study as noted in **section 11**. The date and time of collection of all PK blood samples should be recorded. Validated liquid chromatography/mass spectrometry (LC-MS/MS) methods will be used to assay the samples for plasma concentrations of abemaciclib, abemaciclib metabolites, MK-6482, and MK-6482 metabolites. Additional metabolites, if detected, may be assessed using non-validated methods. Details for the collection, processing, storage, and shipment of samples can be found in the study laboratory manual.

10.2 Pharmacodynamic Assessments

Blood samples collected for serum soluble factors will be assessed for erythropoietin concentration. Whole blood samples will be subjected to DNA isolation to determine genomic status of drug metabolizing enzymes and other hypoxia pathway components that may influence drug exposure and/or response to drug treatment.

11. STUDY CALENDAR

Baseline evaluations are to be conducted within 4 weeks prior to the start of therapy, at the exception of pregnancy test that should be performed within 7 days of therapy start. In the event that the participant's condition is deteriorating, laboratory evaluations should be repeated within 48 hours prior to initiation of the next cycle of therapy.

Assessments must be performed prior to administration of any study agent. Study assessments and agents should be administered within \pm 3 days of the protocol-specified date, unless otherwise noted.

Study calendar is described in **Table 15**.

Table 15. Study calendar.

	Pre-treatment ¹	Cycle 1 ²		Cycle 2 ²		Cycle 3+ ²	Every 8 weeks ³	Treatment discontinuation visit (within 30 days of last treatment) ⁴	Follow-up ⁵	EDC Timepoints
		D1	D15	D1	D15					
Informed Consent										
Demographics	X									Baseline
History and Physical⁶	X	X	X	X	X	X		X		Baseline, every cycle and EOT
ECOG Performance Status	X	X	X	X	X	X		X		Baseline, every cycle and EOT
Vital Signs⁷	X	X	X	X	X	X		X		Baseline, every cycle and EOT
Weight	X	X	X	X	X	X		X		Baseline, every cycle and EOT
Height	X									
Hematology⁸	X	X	X	X	X	X		X		Baseline, every cycle and EOT
Serum Chemistry⁹	X	X	X	X	X	X		X		Baseline, every cycle and EOT
Liver Function Tests¹⁰	X	X	X	X	X	X		X		Baseline, every cycle and EOT
Urine protein/creatinine ratio	X									Baseline
Coagulation Factors¹¹	X									Baseline
Pregnancy Test¹²	X			X		X				Baseline, Cycle 2 D1 and every cycle day 1 after
Viral Serologies¹³	X									Baseline
C-Reactive Protein	X									Baseline
EKG	X									Baseline
ECHO	X									Baseline
MRI or CT Brain¹⁴	X					X ¹⁵				Baseline and every 8 weeks
Imaging¹⁶	X					X				Baseline and every 8 weeks
FKSI-19	X					X	X			Baseline, every 8 weeks and EOT
BFI	X					X				Baseline and

										every 8 weeks
Concomitant Medications	X	X	X	X	X	X		X		Baseline, every cycle and EOT
Adverse Events	X	X	X	X	X	X		X		Baseline, every cycle and EOT
Abemaciclib¹⁷						X				Every cycle
Germline DNA¹⁸		X								C1D1
Archival Tumor Tissue¹⁹	X									Baseline
Tumor Biopsy²⁰	X							X		Baseline and EOT
Pharmacokinetic samples²¹		X								Cycle 1 Day 1
Pharmacodynamic samples²²		X	X							Cycle 1 Day 1 and Cycle 1 Day 15
Survival Follow-Up									X	Follow Up
Arm 2 only										
MK-6482^{23, 24}					X					Arm 2 every cycle

1: Baseline evaluations are to be conducted within 28 days prior to the start of therapy, at the exception of the serum pregnancy test that must be performed within 7 days of therapy start. Scans must be done within 28 days prior to the start of therapy. All baseline screening should be done prior to registration.

2: A cycle will be defined as 28 days.

3: Imaging assessments, quality of life assessments will take place:

- every 8 weeks (+/- 7 days) for the first 6 months.

- After 6 months, imaging assessments and quality of life assessments can take place every 12 weeks (+/- 10 days)

4: Patients who discontinue from treatment will be asked to return to the clinic no more than 30 days after the last treatment for a treatment discontinuation visit. The visit at which a response assessment shows progressive disease may be used as the treatment discontinuation visit.

5: After progression/treatment discontinuation, participants will be followed for survival and receipt of next line therapies every 6 months until death or 2 years after treatment discontinuation. Participants removed from protocol therapy with ongoing treatment-related adverse event(s) will be followed until resolution or stabilization of the adverse event(s), initiation of new cancer-directed treatment, or death. Participants removed from protocol who did not experience disease progression will be followed as per protocol until progression, initiation of new cancer-directed treatment, or death.

6: Physical examination should include general description of participant, head, eyes, ears, nose, and throat, chest, abdominal, extremities, neurologic, skin, and lymph node examination. Any other evaluation is up to the discretion of the practitioner. It will not be considered a violation if the exam is not described as outlined here.

7: Vital signs include blood pressure, heart rate, respiratory rate, body temperature and pulse oximetry.

8: Hematology testing to include full CBC with WBC, ANC, hemoglobin, and platelet count and differential.

9: Serum chemistry to include full comprehensive metabolic panel with sodium, potassium, chloride, bicarbonate, BUN, creatinine, glucose, calcium, albumin, magnesium, and LDH.

10: Liver function tests to include AST, ALT, total bilirubin, and direct bilirubin

11: Coagulation factors to include PT, aPTT, and INR.

12: Pregnancy test only needs to be obtained in women of childbearing potential, within 7 days of therapy start.

13: Hepatitis B virus (HBV) serology (HBsAg, hepatitis B core antibody), and HCV serology (anti-HCV). HBV DNA test is required for patients who have known positive serology for hepatitis B core antibody. HCV RNA test is required for patients who have known positive serology for anti HCV. HIV testing is also required if you are not known to have HIV.

14: MRI of the brain with and without contrast is preferred. If a patient is not able to obtain an MRI, CT imaging with contrast is acceptable. If a patient is no able to receive contrast, CT head without contrast is acceptable.

- 15: Brain imaging should be performed along with other imaging assessments during the study in case the participant has previously treated brain metastases at baseline. Brain metastases at baseline that are untreated, symptomatic, or that require corticosteroids constitute an exclusion criteria.
- 16: Diagnostic CT chest and CT or MRI of the abdomen and pelvis should be obtained at baseline and at every planned assessment. All baseline scans used to determine disease burden should be continued during restaging scans. In instances when providers would like to follow with bone scans they can be followed at 8 or 12 weeks by provider discretion. Actual images and imaging reports at all time points including baseline, on study, and at treatment discontinuation must be sent to DFCI for central review once a patient has discontinued treatment.
- 17: Abemaciclib given twice daily as directed by the principal investigator.
- 18: Blood for germline DNA analysis will be collected once at Cycle 1 Day 1.
- 19: Archival tissue should be requested prior to therapy initiation if available. A note from the study team should be provided documenting availability of tissue.
- 20: Baseline fresh tumor biopsies are not optional, and must occur at least 7 days prior to the first dose of therapy if medically feasible and safe. Progression tumor biopsies are mandatory if medically safe. The progression tumor biopsy must be at least 2 weeks after the participants' last dose of the study drugs.
- 21: At the Cycle 1 Day 1 Visit, patients will have 4mL of blood drawn for PK assessments before and 3 (\pm 15 minutes) hours after study drug administration.
- 22: One blood sample for analysis of PD effects (e.g., EPO) will be collected before study drug administration on Cycle 1 Day 1 and Cycle 1 Day 15. One whole blood RNA sample for RNA expression analysis will be collected before study drug administration on Cycle 1 Day 1 and Cycle 1 Day 15. Two whole blood DNA samples will be collected at the Week 1 Day 1 visit only for sequencing of genes encoding proteins that may be involved in regulating MK-6482 metabolism or in response to the combination treatment.
- 23: MK-6482 given once daily as directed by the principal investigator.
- 24: Patients should hold morning doses of abemaciclib and MK-6482 tablets on clinic visit days on Cycle 1 Day 1 and Cycle 1 Day 15 until after completion of the first blood collection. The time of ingestion of abemaciclib and MK-6482 tablets should be recorded and subsequent time dependent procedures should be performed relative to the MK-6482 dose ingestion time.

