14.1.2 Secondary endpoints

Duration of response (DOR) as defined in section 12.1.4.5.

Progression-free survival (PFS) defined as the time from trial treatment start to the earlier of progression or death due to any cause. Participants alive without disease progression are censored at date of last disease evaluation.

Overall survival (OS) defined as the time from trial treatment start to death due to any cause, or censored at date last known alive.

Safety and tolerability according to NCI CTCAE v5.0.

Quality of life using FKSI-19 and BFI. The FKSI-19 is a 19 item questionnaire with each item scored on a scale of 0-4 for a total score of 0-76 with higher scores indicating fewer symptoms (Appendix D)²⁹. The BFI is a 9 item questionnaire with each item scored on a scale of 0-10. Scores are categorized as mild (1-3), moderate (4-6), or severe (7-10). A global fatigue score can be found by averaging the score obtained on each test item completed (Appendix E)³⁰.

Pharmacokinetics of abemaciclib and MK-6482.

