14.3.5 Quality of Life (QOL) Endpoints Analysis

The QOL will be measured by the Functional Assessment of Cancer Therapy-Kidney Symptom Index (FKSI)-19 and the Brief Fatigue Inventory (BFI). The questionnaires will be administered per schedule defined in section 11 (study calendar).

The FKSI-19 comprises of 19 items (each score ranging from 0-4) with a possible maximum total score of 76. The BFI is a 9 items questionnaire (each score ranging from 0-10) with a possible maximum score of 90. The calculated total scores at each timepoint and changes from baseline will be summarized with mean and standard deviation. Changes from baseline will be graphically presented. For FKSI-19, the proportion of patients with “clinically significant” symptoms (those scoring 3 or 4) will also be descriptively summarized over times across all items or by sub-domains. Missing assessments may be due to stopping treatment, not completing the FKSI or BFI assessments, and other reasons. Information on reasons why the patient did not complete the FKSI-19 or BFI Form will be collected.

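### The BFI, unlike the FKSI-19, is not scheduled at the treatment discontinuation visit, so patients who stop before week 8 may have no post-baseline BFI

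*Combined protocol and SAP*

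**What the plan says.** Section 14.1.2 lists as a secondary endpoint "Quality of life using FKSI-19 and BFI". For timing, section 14.3.5 refers back to the calendar: "The questionnaires will be administered per schedule defined in section 11 (study calendar)".

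In Table 15 the EDC Timepoints entry for the FKSI-19 is "Baseline, every 8 weeks and EOT". The entry for the BFI, on the next row, covers baseline and the 8-weekly assessments and stops there. Footnote 3 sets one interval for all quality-of-life forms: "every 8 weeks (+/- 7 days) for the first 6 months", with 12-weekly assessments (window 10 days either way) permitted after that.

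Section 14.3.5 summarises total scores at each timepoint and changes from baseline, for both instruments, by mean and standard deviation. It recognises that "Missing assessments may be due to stopping treatment" and says that reasons for missing forms will be collected. It does not say how missing scores will be handled.

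**The concern.** The two questionnaires form one endpoint and share the core analysis, yet only one has a closing assessment. No reason is given, so this looks more like an omission than a choice.

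The BFI is the plan's dedicated fatigue instrument, and section 7.1 lists fatigue among the most frequent toxicities of both drugs: 65% with abemaciclib (13% at grade 3) and 67% with MK-6482. Stopping early is plausibly related to how fatigued a patient is. If early stoppers contribute no change score, the summary of BFI change describes mainly those who stayed on treatment to week 8, and worsening is likely to be understated. What is at stake is the reading of a descriptive secondary endpoint. The response rate and the MTD are not affected.

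**Working it through.** The plan states no figure on this point, so there is none to reproduce. The check compares the schedule entries and then shows what the gap could amount to under stated assumptions.

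**Schedule for each fatigue-related measure**

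| Measure | Baseline | On treatment | EOT visit | Source |
|---|---|---|---|---|
| FKSI-19 | yes | every 8 weeks, then every 12 | yes | Table 15, footnote 3 |
| BFI | yes | every 8 weeks, then every 12 | not scheduled | Table 15, footnote 3 |
| Adverse events (CTCAE v5.0) | yes | days 1 and 15 of cycles 1 and 2, then every cycle | yes | Table 15, section 14.3.4 |

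The X marks in the quality-of-life rows may not line up with their columns in a text copy of the table, so this reading rests on the EDC Timepoints column, which is unambiguous.

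**Who is affected**

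1. The earliest on-treatment BFI is at week 8 less the 7-day window: 56 − 7 = day 49, the end of week 7.
2. A patient who stops before then has no scheduled on-treatment BFI and no EOT BFI. Section 5.7 and footnote 5 keep patients who stop without progression in follow-up as per protocol, but do not say whether questionnaires continue. The Follow-up column of Table 15 marks survival only. A later BFI is therefore possible but not scheduled.
3. A patient who stops between assessments, which may be 12 weeks apart after 6 months, has no BFI at stopping.
4. The plan expects some early stoppers: section 5.9 deals with participants who do not reach the 8-week imaging.

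**Illustration (assumed inputs)**

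Let *d* be the share stopping before the first 8-week form with no later BFI. The documents do not give *d*; 10% to 40% is assumed. Patients without a BFI change score = N × *d*, with N from section 14.2:

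| *d* | N = 37 (maximum enrolment) | N = 20 (treated at the MTD) | N = 11 (arm 1) |
|---|---|---|---|
| 10% | 3.7 | 2.0 | 1.1 |
| 20% | 7.4 | 4.0 | 2.2 |
| 30% | 11.1 | 6.0 | 3.3 |
| 40% | 14.8 | 8.0 | 4.4 |

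Let *m*₁ be the mean change in patients with a form and *m*₂ the mean change in early stoppers. The mean over everyone is (1 − *d*)*m*₁ + *d m*₂, whereas the observed mean is *m*₁. The difference is *d* × (*m*₂ − *m*₁). If early stoppers worsen by 2 points more on the 0–10 global score (assumed), the observed mean understates worsening by 0.2, 0.4, 0.6 and 0.8 points for *d* = 10%, 20%, 30% and 40%. With an excess of 1 to 3 points, the range is 0.1 (10% × 1) to 1.2 (40% × 3). On the 0–90 total score in section 14.3.5 these figures are nine times as large.

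**The case against.** A reader might infer from the missing form that fatigue goes unmeasured in early stoppers. The documents do not support that. The FKSI-19 completed at EOT asks about fatigue, lack of energy and general weakness (Appendix D), and adverse events are recorded through every cycle and at EOT. Section 14.3.4 takes the worst CTCAE grade and summarises events that led to discontinuation or dose changes. What is missing is a BFI score; these other measures cannot supply a BFI change from baseline.

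Nor does every later stopper lack a BFI at stopping. Footnote 4 says "The visit at which a response assessment shows progressive disease may be used as the treatment discontinuation visit", and the questionnaires fall due with imaging, so a patient who stops at a scheduled scan has a BFI due then. This does not help those who stop between scans.

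Two further objections stand:

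- **An EOT form does not repair the by-visit summaries.** The week-8 mean would still contain only patients with a week-8 form.
- **The EOT visit is an imperfect time to ask.** It may fall up to 30 days after the last dose, at a different time for each patient, and the BFI severity items ask about now and the past 24 hours. Fatigue that eased after stopping could be missed.

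The stakes are also low. Quality of life is absent from the secondary objectives in section 1.3, the analysis is descriptive, and reasons for missing forms are collected.

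**Conclusion.** The point holds as a minor, inexpensive improvement. The calendar gives the FKSI-19 an EOT assessment and the BFI none, without a reason. Patients who stop before about week 7 may have no post-baseline BFI, and BFI change is summarised mainly in patients who reach week 8.

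The likely direction is understated worsening, on the assumption that early stoppers are on average more fatigued; some will stop for progression or other reasons. The size cannot be derived. Section 14.2 gives only one discontinuation figure for ccRCC, under 10% for adverse events on MK-6482, and that is for the single agent and not tied to week 8. A reader might conclude that a particular fraction of the worsening is hidden, but any such figure would follow entirely from the chosen inputs. The counts and shifts shown above are illustrations only.

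**What to change.** 1. In Table 15, change the BFI timepoints to match the FKSI-19 row, "Baseline, every 8 weeks and EOT", and mark the BFI at the treatment discontinuation visit. If the difference is intended, state the reason.
2. In section 14.3.5, report the EOT (last-assessment) change from baseline for both instruments beside the by-visit summaries, and give the number of patients contributing at each timepoint.

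The cost is one extra 9-item form at a visit where the FKSI-19 is already completed, plus a calendar and EDC edit. The gain is limited to patients who attend that visit and complete the form. The EOT change should be presented as a separate summary taken at varying times after the last dose, because it does not correct the week-8 mean.
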